Effects of Vitamin D and Omega-3 on Cerebrovascular Disease

NCT04070833

August 13, 2021

Summary

Recently, there has been growing interest in the role that vitamin D as well as omega-3 fatty acids play in the development of cardiovascular disease events. The NIH sponsored VITamin D and OmegA-3 TriaL (VITAL) is a randomized, double blind trial testing vitamin D₃ and omega-3 fatty acid supplementation in the primary prevention of cancer and cardiovascular disease. I will leverage this trial to determine the impact of vitamin D₃ and omega-3 fatty acid supplementation on stroke outcomes.

The current research study summarized in this protocol will collect additional information on stroke outcomes which is not obtained by the parent VITAL study. To obtain this information, participants who experience a stroke will receive a questionnaire assessing functional status, functional limitations, physical disability, and social disability at 6 and 12 months after the stroke. This is the only additional information being collected as part of the current research study.

Data from this study will allow us to determine whether vitamin D₃ and omega-3 fatty acid supplementation reduces the risk for poor outcomes after a stroke event.

I. Background and Significance

Global burden of stroke.

Stroke is a leading cause of disability and death worldwide and is expected to become an even more prevalent cause of disability in the future as the population ages.^{1, 2} Understanding risk factors which may prospectively influence stroke outcomes may help to reduce the morbidity burden of stroke.

Vitamin D and omega-3 fatty acids and incident stroke.

Recently, there is growing interest in the effect of vitamin D and omega-3 fatty acids on cardiovascular disease risk. A recent meta-analysis of observational studies found that individuals with the lowest serum 25-hydroxyvitamin D (25(OH)D) levels had a relative risk of 1.64 (1.27-2.10) for stroke compared to those with the highest levels.³ In contrast, a meta-analysis of randomized trials of vitamin D supplementation did not find an effect on stroke risk (RR=1.05)⁴; however, the levels of supplementation tested in the trials were low.⁵ Omega-3 fatty acid intake was associated with reduced risk of stroke among healthy individuals in a meta-analysis of observational studies.⁶ No published large randomized trials of marine omega-3 fatty acids for the primary prevention of CVD in the general population exist. Randomized trials of omega-3 fatty acid supplementation among patients with cardiovascular disease (CVD)^{7, 8}, hypercholesterolemia⁹, or dysglycemia¹⁰ observed no effect on stroke risk.

Impact of vitamin D and omega-3 fatty acids on stroke outcomes: Gaps in knowledge. Information on the effect of vitamin D and omega-3 fatty acid supplementation on stroke outcomes (as opposed to incident stroke) in healthy populations is limited. Studies among stroke patients observed that lower levels of 25(OH)D at hospital admission predict infarct volume¹¹, initial stroke severity and handicap at hospital discharge¹², as well as death and functional outcome at 90 days post-stroke.¹³ However, these studies cannot test if supplementation with vitamin D in healthy populations impacts stroke severity and functional outcomes post-stroke. Several hypotheses have been formulated to explain how vitamin D may impact stroke outcomes. Vitamin D may have neuroprotective properties¹⁴ and 25(OH)D may promote neuroplastic changes which improve recovery after stroke.¹² Additionally by preserving bone, restoring muscle strength, reducing falls, and protecting against cognitive impairment and depression, vitamin D may assist in post-stroke recovery.^{15, 16} Less is known about the impact of omega-3 fatty acid supplementation on stroke outcomes. An animal study observed that a DHAenriched diet protected against post-ischemic inflammation and injury in the brain.¹⁷ This suggests that DHA may protect against the immune response or brain damage in ischemic stroke and may result in improved stroke outcomes.

Opportunity to determine the impact of vitamin D and omega-3 fatty acids on stroke outcomes. The ongoing VITamin D and OmegA-3 TriaL (VITAL) (this parent study is approved by Partners IRB, Protocol #2009P001217/MGH) will examine the impact of vitamin D₃ (2,000 IU/day cholecalciferol) and omega-3 fatty acids (840 mg eicosapentaenoic acid [EPA] + docosahexaenoic acid [DHA]) on stroke incidence. Given the high morbidity burden of stroke, the impact of these supplements on stroke outcomes is of substantial scientific and public health importance. This proposal will collect additional data to determine the effect of these supplements on post-stroke outcomes. Even if they do not significantly reduce stroke incidence, they may still reduce stroke severity and improve outcomes post-stroke. The randomized doubleblind design among healthy adults will provide the highest quality data on the impact of these agents on long-term stroke outcomes.

II. Specific Aims

The primary specific aim of this study is to test whether vitamin D₃ or omega-3 fatty acid supplementation reduces the risk of poor functional outcomes as measured at hospital discharge and 6- and 12-months post-stroke (~400 strokes in VITAL).

III. Subject Selection

Participants will be selected from the VITAL study. VITAL is a NIH-funded (CA138962 with support also included from NHLBI) randomized, double-blind, placebo-controlled trial to test the effects of vitamin D₃ (cholecalciferol, 2,000 IU/d) and omega-3 fatty acid (840 mg/d of EPA/DHA [ratio of 1.3:1]) supplements in the primary prevention of CVD and cancer in a multiethnic population of 25,875 individuals.¹⁸ The trial enrolled men aged \geq 50 and women aged \geq 55 without a history of cancer (except non-melanoma skin cancer), myocardial infarction, stroke, transient ischemic attack, or coronary revascularization. All subjects signed a detailed informed consent form, agreed to limit consumption of supplemental vitamin D and calcium to no more than 800 IU/d and 1200 mg/d respectively and to forgo use of fish-oil supplements during the trial. This ongoing parent study is approved by Partners IRB, Protocol #2009P001217/MGH. Additionally, VITAL received IND approval from the FDA on March 11, 2011 (IND #105558) and is registered on clinicaltrials.gov (NCT01169259).

Our specific aim examines the influence of randomized treatment assignment on risk of functional outcomes from stroke at 6 and 12-months after stroke. For this component, we will include only individuals in VITAL who experienced a stroke event.

IV. Subject Enrollment

For the VITAL participants who report a stroke event, at 6 and 12-months after their reported stroke event, we will invite them to complete an additional questionnaire asking about their current limitations in everyday activities. For non-responders, a second request will be made. Consent to participate will be implied by completing the questionnaire.

V. Study Procedures

Stroke Outcomes Assessment in VITAL

The parent VITAL trial collects information on stroke severity at hospital discharge as measured by the modified Rankin scale (mRS). We will send additional follow-up questionnaires at 6months and 12-months post-stroke to assess stroke outcomes for all participants who experience a stroke. This information is not collected by the parent study and will only be collected by this study. Assessing outcomes at 6 and 12-months will allow us to determine initial stroke recovery as well as further improvements or sustained functioning. The stroke outcome questionnaires will include the same functional assessment questions as the baseline questionnaire in the parent study to allow for comparisons to baseline functional status. These questions assessed baseline physical function and limitations in: vigorous or moderate activities; lifting or carrying groceries; climbing stairs; bending, kneeling, stooping; walking >1 mile; walking several blocks; or walking 1 block. Respondents are also asked if they received help with feeding themselves, dressing, getting in and out of bed, and taking a bath or shower.

In addition, I will ask several questions originally developed and used by the Framingham Heart Study (FHS) to assess functional limitations, physical disability, and social disability among individuals with stroke.^{19, 20} Functional limitations will be assessed through the physical performance scale adapted from Nagi²¹ and physical disability with the modified Katz Activities of Daily Living (ADL) Scale²² and the Rosow-Breslau Functional Health Scale.²³ These measures have high test-retest reliability.²⁴⁻²⁹ The adapted Nagi scale asks respondents if they experience limitations in: pulling or pushing large objects; stooping, crouching, or kneeling; reaching or extending arms above shoulder level; reaching or extending arms below shoulder level; writing or handling or fingering small objects; standing in one place for long periods; and sitting for an hour. The Rosow-Breslau Functional Health Scale asks if the respondent needs help with the following gross mobility tasks: walking 0.5 mile; walking up and down stairs to the second floor; and doing heavy work around the house. The modified Katz ADL scale asks about needing help with: bathing; dressing; eating; getting in and out of a chair; and walking 50 yards. I will also ask participants if they are completing the questionnaire themselves or if it has been completed by a proxy respondent and if they currently reside in a nursing home. I will create cumulative disability scales similar to those previously developed in stroke survivors in FHS.¹⁹ First, I will dichotomize responses to each item as unlimited (no limitation or no help needed) versus limited (any amount of limitation or help needed). Next, each scale (Nagi, Katz, and Rosow-Breslau) will be dichotomized into unlimited (no limitation in any of the items) versus limited (limitation in at least one item). Finally, I will create a cumulative disability index with values of 0 (no limitation on any scale), 1 (limitation on Nagi scale only), 2 (limitations on Nagi and Rosow-Breslau scales), and 3 (limitations in all three scales).

Social disability will be assessed using a scale also developed in the FHS²⁰ which incorporates both need for assistance and unmet need for assistance. Someone with a need for assistance is not self-sufficient in performing the activity, but is able to find support to meet this need. In contrast, those with an unmet need are not able to find this support. The scale covers five social areas (housekeeping, transportation, social interaction, food preparation, and grocery shopping). Respondents are grouped into four categories (need met, no apparent problem; need met, potential problem; uncertain need met, potential problem; need unmet, current problem) for each social area using a previously published algorithm.²⁰ I will examine each social area individually and create summary indices for the total number of unmet needs across all areas and for the total number of unmet needs or uncertain needs met, potential problem. These indices range from 0 to 5, but to avoid problems with model convergence due to sparse data I will *a priori* categorize them as 0, 1, or ≥ 2 .

VI. Biostatistical Analysis

We will use logistic regression to examine the effects of randomized treatment assignments in VITAL on functional limitations, physical disability, and social disability using separate models

for each outcome as defined above. Only individuals with a completed stroke outcomes questionnaire will contribute to these analyses. We will perform analyses for total stroke as well as for the ischemic strokes only. For the analysis of functional limitations and physical disability, we will also perform a sensitivity analysis in which we restricted to those individuals who did not report functional limitations at baseline in VITAL.

We will also perform a sensitivity analysis in which we will use inverse probability of treatment weights to adjust for potential differences between treatment groups since our analysis conditions on experiencing a stroke event. We will first develop a propensity score for randomized treatment assignment at the time of stroke including information on age at randomization, sex, body mass index, physical activity, statin use, alcohol consumption, history of hypertension, history of high cholesterol, race, and smoking status to predict treatment assignment. We will then use weighted logistic regression to estimate the association between randomized treatment and our outcomes. We will perform an additional sensitivity analysis in which fatal stroke events were included as the worst possible outcome category.

References

McKay J, Mensah GA. Atlas of Heart Disease and Stroke: World Health Organization;
2004.

7. Dietary supplementation with n-3 polyunsaturated fatty acids and vitamin E after myocardial infarction: results of the GISSI-Prevenzione trial. Gruppo Italiano per lo Studio della Sopravvivenza nell'Infarto miocardico. Lancet. 1999;354(9177):447-55.

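### Scoring each disability scale as any limited item versus none hides change within a scale and costs precision if limitation is common; analyse the 0–3 index as ordinal and add item counts

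*Combined protocol and SAP*

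**What the plan says.** Section V (Study Procedures, Stroke Outcomes Assessment in VITAL) scores the three physical scales in steps, following a method used earlier in Framingham stroke survivors.

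- Item level: "First, I will dichotomize responses to each item as unlimited (no limitation or no help needed) versus limited (any amount of limitation or help needed").
- Scale level: "each scale (Nagi, Katz, and Rosow-Breslau) will be dichotomized into unlimited (no limitation in any of the items) versus limited", where one limited item is enough. As listed, Nagi has 7 items, Rosow-Breslau 3 and Katz 5.
- Across scales: a cumulative index is formed, running from 0 (no scale limited) through 1 (Nagi only) and 2 (Nagi and Rosow-Breslau) to 3 (all three).

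Section VI (Biostatistical Analysis) says "We will use logistic regression to examine the effects of randomized treatment assignments", with a separate model for each outcome as defined in Section V. It does not say whether the four-level index is modelled as ordinal, as multinomial or after a further cut. No item count is planned for the physical scales. For social disability, by contrast, Section V counts problem areas from 0 to 5 and pools them in advance to 0, 1 and 2 or more because of sparse data. The plan gives no expected prevalence of limitation, no response rate and no power calculation. The only size given is about 400 strokes (Section II), and only people who complete a questionnaire are analysed.

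**The concern.** Section I argues that even if the supplements do not prevent strokes, "they may still reduce stroke severity and improve outcomes post-stroke". Section V adds that the 6- and 12-month forms should show initial recovery and later improvement. A per-scale dichotomy registers a benefit only when it moves someone between no limited item and at least one. Going from six limited Nagi items to one leaves the code unchanged. In the sensitivity analysis that counts fatal stroke as the worst category (Section VI), a dichotomised scale would give death the same code as slight difficulty kneeling.

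Participants were at least 50 (men) or 55 (women) at entry and have since had a stroke, so the Nagi scale in particular could have few people in its unlimited category. With at most about 400 strokes, and fewer returned forms, precision is already scarce. A null result on a nearly saturated binary outcome would be hard to interpret.

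**Working it through.** The plan states no power or precision figure, so there is none to reproduce.

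**Inputs from the plan.** Item counts of 7, 3 and 5; about 400 strokes as a ceiling; completers only.

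**Assumptions.** 300 completers; equal allocation; two-sided 5% and 80% power (1.96 + 0.84 = 2.80); proportional odds; prevalence *p* of any limitation varied from 40% to 90%. Item responses follow a logistic random-effect model (SD 2, item difficulties spread over ±1.5) tuned to give *p*.

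**Formulas.** With category proportions *p_i*, the information on the log odds ratio is *N·e*/12, where *e* = 1 − Σ*p_i*³. For a dichotomy this is *e* = 3*p*(1 − *p*). The detectable odds ratio is exp(−2.80/√(*N·e*/12)).

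**Worked case, Nagi, 80% limited.**
- Dichotomy: *e* = 3 × 0.8 × 0.2 = 0.48; exp(−2.80/√12) = 0.45.
- Count 0–7: *e* = 0.98; exp(−2.80/√24.5) = 0.57.
- Ratio: 0.48/0.98 = 0.49, so 300 binary observations are worth about 147 ordinal ones.

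| Limited | *e*, dichotomy | Information kept, Nagi | Information kept, Rosow-Breslau | Detectable OR, dichotomy |
|---|---|---|---|---|
| 40% | 0.72 | 93% | 94% | 0.52 |
| 60% | 0.72 | 78% | 80% | 0.52 |
| 70% | 0.63 | 66% | 68% | 0.49 |
| 80% | 0.48 | 49% | 51% | 0.45 |
| 90% | 0.27 | 27% | 30% | 0.34 |

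For Katz at 40% limited the loss is about 7%.

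**Bound that needs no item model.** A count cannot exceed *e* = 1 − (1 − *p*)³, so the loss cannot exceed 1 − 3*p*(1 − *p*)/[1 − (1 − *p*)³]. At 40% this is 1 − 0.72/0.784 = 8%; at 80%, 1 − 0.48/0.992 = 52%; at 90%, 1 − 0.27/0.999 = 73%. The modelled losses lie close to these limits.

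**The 0–3 index as ordinal.** Take Nagi 80%, Rosow-Breslau 70% and Katz 40% limited, and score the number of limited scales. The item model then spreads people about 14/19/31/36%.
- Σ*p_i*³ = 0.003 + 0.007 + 0.030 + 0.047 = 0.086, so *e* = 0.91 and the detectable OR is exp(−2.80/√22.8) = 0.56.
- Section V gives a value to only four of the eight possible scale patterns. Dropping the others (about 9% of people here) gives 0.54.
- With Nagi and Rosow-Breslau at 90% and Katz at 80%, the spread is about 4/7/14/75%, *e* = 0.575, and the detectable OR falls to 0.48.

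**What a shift would look like (illustrative, 200 per arm).** Let the index be 15/20/25/40% on control and 15/35/30/20% on treatment.
- Nagi: 85% limited in both arms, OR 1.00.
- Rosow-Breslau: 65% against 50%, OR = (0.50/0.50)/(0.65/0.35) = 0.54.
- Katz: 40% against 20%, OR = (0.20/0.80)/(0.40/0.60) = 0.38.
- Index: about 95% power with a rank test.

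Now let the shift lie wholly within Katz: 40% limited in both arms, but mostly 4–5 limited items on control and mostly 1–2 on treatment. The Katz dichotomy does not move, and the index is unchanged in this example. The Katz count sees the shift, though with only about 25% power.

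**The case against.** The strongest reply is that the plan does not rest on the three dichotomies alone. A reader might infer that the 0–3 index inherits their ceiling, so that a move from severe to mild disability is hidden throughout. The documents do not support that. The index reaches its top level only when Katz is limited as well, so saturation of Nagi does not saturate it. In the first example above, the index and two of the three dichotomies show the shift. What stands against this reply is that the index helps only if its order is used. The three-level social indices and the worst-category analysis for fatal strokes suggest multi-level models, but Section VI never says so.

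A reader might also quote a fixed loss, such as a third to three quarters of the information. That range needs 70–90% limited. No prevalence is given, and entry age alone does not establish one. The sensitivity analysis restricted to people without baseline limitation also removes some limitation that predates the stroke, at the price of a smaller sample.

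Other points are fair. The specific aim concerns the risk of poor functional outcome, and graded severity at discharge is captured by the modified Rankin scale. Using a published scoring rule is defensible in itself, even with no Framingham comparison planned. A count of limited items still keeps the item-level cut: slight difficulty on seven items outscores complete inability on three. These points weigh against making item counts the main outcome and demoting the index. They do not weigh against adding the counts.

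**Conclusion.** The point holds for the per-scale outcomes. Change in severity within a scale cannot be seen, and precision is lost to a degree that depends on an unstated prevalence. The loss relative to the item count is about 7% at 40% limited, 20–22% at 60%, a third at 70%, half at 80% and 70–73% at 90%. At 300 completers and 80% limited, the detectable odds ratio is about 0.45 against 0.57. The prevalences, the number of completers, the item model and proportional odds are all assumptions. The bound above shows that the item model matters little for the largest possible loss.

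For the plan as a whole the problem is smaller. An ordinal analysis of the index recovers most of the precision (about 0.56, or 0.54 on the defined patterns only) unless Katz is also largely limited. The documents support a cheap improvement and a needed clarification. They do not show that the plan is blind to severity or that the published scoring must be replaced.

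**What to change.** In Section VI:

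1. State that the 0–3 cumulative index is analysed by proportional-odds logistic regression, and in Section V give a value to every scale pattern so that no completer is left unscored.
2. For each scale, add a pre-specified proportional-odds analysis of the number of limited items (Nagi 0–7, Rosow-Breslau 0–3, Katz 0–5). Pool sparse upper levels by a rule fixed before unblinding, as is already done for social disability.
3. Keep the any/none dichotomy for consistency with the published scoring.
4. State the expected prevalence of limitation on each scale, or a range, so that readers can judge the precision of each outcome.

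The cost is some wording and a little more analysis. The items are already collected, so no new data are needed. The drawbacks are a proportional-odds assumption that must be checked and a contrast less simple to report than any limitation versus none.

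### No full-sample analysis accounts for baseline physical function: the main models name no covariate, and the propensity score meant to correct for conditioning on stroke leaves it out

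*Combined protocol and SAP*

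**What the plan says.** All references are to the combined protocol and SAP.

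- **Main models (VI. Biostatistical Analysis).** The model statement reads: "We will use logistic regression to examine the effects of randomized treatment assignments in VITAL on functional limitations, physical disability, and social disability", one model per outcome. No baseline covariate is named. The plan does not say the models are unadjusted; it is silent.
- **Analysis set (VI).** "Only individuals with a completed stroke outcomes questionnaire will contribute to these analyses".
- **Weighted sensitivity analysis (VI).** Inverse probability weights are used "to adjust for potential differences between treatment groups since our analysis conditions on experiencing a stroke event". The propensity variables are "age at randomization, sex, body mass index, physical activity, statin use, alcohol consumption, history of hypertension, history of high cholesterol, race, and smoking status". The weighted outcome model names no further covariate.
- **Restricted sensitivity analysis (VI).** "For the analysis of functional limitations and physical disability, we will also perform a sensitivity analysis"; it is described as a "sensitivity analysis in which we restricted to those individuals who did not report functional limitations at baseline in VITAL". Social disability is not included.
- **Fatal-stroke sensitivity analysis (VI).** No covariate is named.
- **What is measured (V. Study Procedures).** The follow-up questionnaires contain the "same functional assessment questions as the baseline questionnaire in the parent study to allow for comparisons to baseline functional status". The outcome scales come from a separate set: "In addition, I will ask several questions originally developed and used by the Framingham Heart Study (FHS) to assess functional limitations".

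**The concern.** The outcomes are limitation and disability after stroke, and function before the stroke is an obvious candidate predictor of them. In the whole randomized cohort, leaving it out would mainly cost precision. This analysis set is different: it consists of people who had a stroke and then returned a questionnaire, both of which happen after randomization. Balance on baseline function is therefore not guaranteed. The plan accepts this argument for stroke, since that is its stated reason for the weighting, but the weighting then omits the baseline measure closest to the outcomes.

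If the arms do differ in baseline function, the full-sample estimates carry the difference. The weighting removes it only as far as listed variables such as physical activity stand in for function. For social disability, no planned analysis uses baseline function at all. Section V repeats the baseline items so that comparison with baseline is possible, yet Section VI makes no such comparison in the full sample.

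**Working it through.** **1. Where baseline function enters Section VI**

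| Analysis | Sample | Baseline function used? |
|---|---|---|
| Main logistic models | All questionnaire completers | No covariate named |
| Propensity-weighted | All completers | Not among the ten variables |
| Fatal stroke as worst category | Completers plus fatal strokes | No covariate named |
| No baseline limitation | Subset | Yes, by restriction; social disability not covered |

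The baseline items overlap with the outcome scales (stairs, stooping, bathing, dressing) but are not identical to them. A baseline score is thus a related prognostic measure, not the baseline value of the outcome.

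**2. Inputs for the size**

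The documents give about 400 expected strokes (II. Specific Aims) and no power, effect size, response rate or prevalence of baseline limitation, so there is no stated figure to reproduce. Assumed: n = 200 to 400 respondents, 1:1 arms, share limited at baseline p = 20 to 60%, OR linking baseline limitation to outcome 2 to 8, control risk 50%.

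**3. Effect of an imbalance when treatment does nothing**

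Let r1 and r0 be the outcome risks in people limited and not limited at baseline, and let the limited share be p + d/2 in one arm and p − d/2 in the other. Each arm's risk is share × r1 + (1 − share) × r0.

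Example: p = 40%, baseline OR 4, d = 10 points. An overall risk of 50% requires r0 = 0.367 and r1 = 0.699.
- Arm with 45% limited: 0.45 × 0.699 + 0.55 × 0.367 = 0.517.
- Arm with 35% limited: 0.35 × 0.699 + 0.65 × 0.367 = 0.483.
- Unadjusted OR = (0.517/0.483)/(0.483/0.517), about 1.14.

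Over the whole range the OR is 1.07 to 1.21 for d = 10 points and 1.03 to 1.10 for d = 5 points.

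A simulation with n = 300, 35% limited, 40% risk in unlimited controls, baseline OR 3 to 8 and a systematic gap of 5 to 10 points gave unadjusted median ORs of 1.06 to 1.18 and type I error of about 7 to 13%. The adjusted model gave about 1.00 and 5 to 6%.

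**4. What the planned weighting would leave**

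Suppose the listed variables reflect function only through a binary proxy with correlation φ to it. The share of the log-OR bias left after weighting is 1 − φ²: 0.91 at φ = 0.3 and 0.75 at φ = 0.5. For the 10-point gap, ORs of 1.06 to 1.19 or 1.05 to 1.15 remain.

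**5. Imbalance by chance**

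The SD of the arm difference is √(4p(1 − p)/n). At n = 400, p = 20% it is √(0.64/400) = 4.0 points; at n = 200, p = 40% it is √(0.96/200) = 6.9 points. A difference of 10 points or more, in either direction, has probability 1 to 15% over the range.

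**6. Precision**

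Power was simulated with 4,000 trials per setting, conditional treatment OR 0.5 and a two-sided 5% Wald test, comparing treatment alone with treatment plus baseline limitation:

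| Baseline OR | Change in power (points) |
|---|---|
| 2 | −0.4 to +0.8 |
| 4 | 1.7 to 4.0 |
| 8 | 4.5 to 10.2 |

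At n = 300, 40% limited and baseline OR 4, power rises from 76.2% to 79.3%. Adjusted type I error was 4.5 to 5.1%.

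**7. Cost of relying on restriction**

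With 20 to 50% limited at baseline, restriction keeps 150 to 240 of 300 respondents. In a simulation with n = 300, 35% limited, 40% risk in unlimited controls and baseline OR 8, power was 66% unadjusted, 77% adjusted in the full sample and 62% restricted.

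**The case against.** The other side has several fair points.

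- **Chance imbalance is not bias.** The unadjusted test already allows for it; null simulations with chance imbalance only gave type I error of 5.0 to 5.6%. This stands. The ORs in step 3 are bias only if the imbalance is systematic.
- **Systematic imbalance through stroke incidence needs a specific mechanism.** Strokes are rare (400/25,875 = 1.5%), so a uniform relative effect on stroke leaves function about balanced among cases. The relative effect would have to differ by baseline function, by a ratio of about 1.5 to 1.9 for a 10-point gap: for p = 40%, (0.45/0.55)/(0.35/0.65) = 1.52. For 5 points it is 1.2 to 1.4. This stands too, although differential survival or questionnaire return by arm are other routes.
- **The bias is small beside sampling error.** The SE of the log-OR at 50% risk is √(16/n), or 0.20 to 0.28, so even a 10-point gap is 0.2 to 0.9 SE. Correct, and a reason not to rate the point higher.
- **It is partly handled.** The restriction is sound for new limitation, and the propensity list includes physical activity. But the restriction uses a subset and leaves out social disability, and activity is a different construct from limitation or needing help. The single-proxy figure in step 4 does not represent ten variables jointly and is illustrative.
- **Baseline is not the moment before stroke.** The items were asked at parent-trial baseline, and the documents give no interval to the event. This weakens the measure's prognostic value but does not remove it.
- **Adjustment changes the estimand.** True: the conditional OR is a different quantity and must be labelled as such.

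These points limit the size. They do not explain why a propensity score built to correct for selection should omit a collected and closely related measure.

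**Conclusion.** The concern holds as a matter of text: no full-sample analysis in Section VI uses baseline physical function, and for social disability no analysis uses it at all. The plan should be changed, but this is not a fatal flaw.

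The size is uncertain because the documents give neither the prevalence nor the prognostic strength of baseline limitation, and they show no actual imbalance. Under the assumed ranges, a systematic gap of 5 to 10 points would move a null OR to between 1.03 and 1.21. The precision gain is negligible unless function is strongly prognostic. The conclusion that function should be included does not depend on these figures. Adjustment would not correct imbalance in unmeasured factors.

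**What to change.** In Section VI:

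1. Pre-specify a baseline physical-function score (the number of limited items on the parent-trial baseline questionnaire) and age at randomization as covariates in the full-sample 6- and 12-month models, including those for social disability. Age is already in the propensity list.
2. Add the function score to the propensity model.
3. Keep the restriction to people without baseline limitation as the sensitivity analysis it already is.
4. State that the adjusted OR is conditional, and report the unadjusted OR or a standardised risk difference beside it.

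The cost is plan wording only, since the parent trial already holds the data. Two covariates are unlikely to strain binary models: in null checks at n = 150 (15% or 30% risk) and n = 250 (15% risk), none of 1,500 fits per setting failed to converge, and adjusted type I error was 3.7 to 4.8%. Those checks did not cover the three-level social indices or the ischemic-only analyses, so sparseness should be checked there before the models are fixed.
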